**Sample Size:**

Our sample size is designed to ensure that we are highly powered to detect a clinically meaningful difference in the co-primary outcomes of opioid dose and pain (PEG) at 12 months. With 172 participants (86 per intervention arm) we will have >90% power to detect a 20mg mean difference in opioid dose between intervention groups assuming a 34 mg SD (based on data from KPWHRI participants meeting entry criteria) and a two-sided, two-sample equal-variance t-test. Assuming the mean baseline dose in our study population to be 67mg MED, this 20mg difference represents a clinically meaningful 30% reduction. Further, given our

sample size of 172 participants we will have approximately 90% power to detect a 1.2 point difference in the PEG between intervention groups, assuming a standard deviation of 2.5. To ensure adequate power given potential loss to follow-up we inflated our final sample size by 25% yielding a target randomization of 215 participants. This will also allow some pre-specified sub-group analyses to look for heterogeneity of treatment effect, as described below. Sample and power calculations were conducted using PASS software Version 14.

b. Sharing of Results with Subjects

Describe whether results (study results or individual subject results, such as results of standard or research lab tests and genetic tests) will be shared with subjects or their providers.

If the study carries a risk of incidental findings, describe your plan for evaluating these and determining whether and how subjects or their providers will be given this information.

If laboratory results will be shared with subjects or their healthcare providers, verify that the laboratory conducting the test is Clinical Laboratory Improvement Amendments (CLIA) certified. We will not be sharing study results with participants

We will be communicating some study information with providers, however we will not be sharing study results with the provider

- If a participant is enrolled in the intervention arm, the provider will be notified of their participation by the study team
- The research interventionist will pass provide a medication recommendation to the PCP using Epic Telephone Encounters. Additionally, any study information that is collected as part of the telephone visit which the research interventionist feels may be important to either support the taper or supplements clinical care may be shared with the provider. This will continue through the course of the taper for patients electing to try the taper support.

c. Data and/or Specimen Banking

Indicate if specimens may be used for future research and whether that may include genetic research.

State if data or specimens will be sent to a separate repository. If data or specimens will be banked in a repository for future use as part of this protocol submission address the following questions:

- What will be banked and what identifiers will be associated with the data or specimens?
- Where and how will the data or specimens be stored?
- For what purpose will the data or specimens be used?
- How will the data or specimens be accessed, and who will have access?
- Describe the procedures to release data or specimens, including the process to request a release, approvals required for release, who can obtain data or specimens, and the data to be provided with specimens.

N/A we will be not banking data or specimens for this project

## 7. Privacy, Confidentiality and Data Security

Describe the steps that will be taken to protect subjects' privacy during recruitment, consent and study procedures.

### Recruitment, Screening and Consent

During all recruitment, screening and consent telephone calls, the study team will confirm the identity of the participant by asking for their full name and DOB. All recruitment and screening calls will take place in the Kaiser Permanente Washington Health Research Institute (KPWHRI) offices; this ensures that work computers are secure and assumes that surrounding colleagues are trained in standard research privacy and confidentiality procedures. We will use REDCap hosted at KPWA to collect patient reported data and intervention visit data; it is 21 CFR Part 11, FISMA, and HIPAA-compliant.

### Intervention

All intervention telephone visit calls will be made at KPWHRI offices (see above). Intervention study visit information will be collected using REDCap which is 21 CFR Part 11, FISMA, and HIPAA-compliant.

a. Describe the plan for storage of data and/or specimens.

- Who will have access and how.
- Where the data/materials will be stored and for how long.
- What identifiers will be included.
- Any other steps that will be taken to ensure security (e.g., training of staff, authorization of access, password protection, encryption, physical security, and separation of identifiers from data and specimens, certificates of confidentiality).
- Describe the plan to deidentify data, destroy data, or retain/archive data at the end of the study.

Analytic study data will be stored at KPWA indefinitely. The linking file and files with PII needed for recruitment and participant contact (names, DOB, address, telephone number, email) will be stored at KPWA on the project G: drive and then destroyed by 12/31/2026. Analytic data files will be stored on the project G: drive. REDcap will be stored on KPWA servers while data collection is ongoing. When REDCap data collection has been completed, QA'ed and cleaned, that data will be exported to the project G: drive and merged with other data sources to create the analytic dataset. Data will be accessible to the study team whose access is controlled by the study project manager and [name].

Additional steps to ensure data security include:

- All KPWA staff are required to have current Human Subjects Research Training
- All KPWA staff are required to have privacy and confidentiality training when they onboard employment
- All KPWA computers are password protected in secure office building where workspace is accessible by key cards

- REDCap access requires a study specific URL to access it and requires a user login/password to authenticate and login
  - REDCap is 21 CFR Part 11, FISMA, and HIPAA-compliant.
- The project has a Certificate of Confidentiality from the National Institutes of Health

b. Collection of data from subjects electronically

If you will collect any data from participants electronically (including email, website, etc.), explain:

- How the data will be collected.
- How the information will be secured (encryption, password protection, etc.; may require consultation with IT department).
- Any risks to the participants' privacy posed by using these methods (describe in consent, as applicable).
- **How you will verify the participant's identity.**

Participants who elect to take their surveys (at baseline, 6 and 12 months) on the internet will complete their survey in REDCap.

When the participant's survey is due (at baseline, 6 and 12 months) the system will trigger an email that sends a link that is specific to the individual recipient.

Similarly, in the intervention arm, participants who elect to take their pre-visit GCPS and HADS surveys on the internet will be emailed a link to take the surveys online. (See "Master Survey Doc")

There will be no further authentication steps to verify the participant's identity.

As stated in above sections, there are many technical, physical and administrative safeguards in place for both REDCap and the servers that REDCap is stored at KPW.

The consent form adequately explains the risks of using email for study research and asks participants to opt-in or out of receiving study emails for web survey administration.

c. Does this study involve the disclosure of PHI to a collaborator?

If any data will be sent outside of this site, list each recipient (may list by role or category if the information is the same for several different entities). For each recipient, describe:

- What will be sent.
- Whether the information will be fully identifiable (PHI, if health information), a Limited Data Set, de-identified, or aggregate.
- How the data/materials will be transferred securely (for instance, Secure File Transfer).

This study will disclose PHI to the University of Washington; Drs. [name] and [name].

We will send audio files of intervention sessions to [name] and these files may contain PHI.

Additionally, Drs. [name] and [name] will receive dates, such as medication dispensing dates, intervention visit dates, and diagnosis dates.

The information sent to Drs. [name] and [name] will be in the form of 1) a limited data set during analyses and 2) the participant tracking database in REDCap, where [name] will be able to view the intervention visit information for each participant and PII will not be displayed/made visible to him. He can view the data in REDCap, but cannot export it.

[name] will have EPIC read only access. He will access EPIC from the KPWHRI hotel stations, inside the KP firewall.

With regard to data transfer security, analytic datasets and audio files will be transferred to Drs. [name] and [name] using the KPWA secure file transfer site (SFTS). This SFTS is housed on KPWA servers. Main analyses will occur at KPWHRI.

When the audio files are transferred to [name] at UW, she will store the files on a UW network drive on her UW office computer. This resides inside the UW firewall. Physically, this computer resides at [name] personal office which is kept locked when she is not present. The computer is password protected and meets all UW Medicine and UW regulations and policies. The UW has security controls in place to prevent the unauthorized access and monitors for unauthorized access.

With regard to the participant tracking database, REDCap is also housed on KPWA servers.

## 8. Provisions to Monitor Data to Ensure the Safety of Subjects

This is required when research involves more than Minimal Risk to subjects.

The plan might include establishing a data monitoring committee and a plan for reporting data monitoring committee findings to the IRB and the sponsor.

Describe:

- Who will monitor the study data for safety?
- The plan to periodically evaluate the data collected regarding both harms and benefits to determine whether subjects remain safe.
- What data are reviewed, including safety data, untoward events, and efficacy data.
- How the safety information will be collected (e.g., with case report forms, at study visits, by telephone calls with participants).
- The frequency of data collection, including when safety data collection starts.
- The frequency or periodicity of review of cumulative data.
- Criteria for taking action on monitoring findings (for instance, stopping rules, immediate suspension, reporting, protocol changes, changes to monitoring frequency or plan).
- For studies monitored by a DSMB/C, describe the committee membership and structure, meeting format, and quorum requirements. Upload the board/committee charter, if one exists.

To monitor risks of the interventions and any need to stop the trial early, we have will create a Data Safety Monitoring Committee (DSMC). This committee will be composed of [name]

[name] (general internist and Head of the Pain Division of the Department of Anesthesiology and Pain Medicine at the University of Washington), [name] (anesthesiologist and pain medicine expert practicing at Harborview Medical Center in Seattle) and [name], a biostatistician and Associate Professor, Psychiatry and Behavioral Sciences, University of Washington, with experience in data analysis and design of RCTs. [name] will serve as the chair of the committee while Drs. [name] and [name] will be members. This committee will meet during the pre-intervention phase and annually to review the protocol, data collection and data completeness. A quorum is defined as all three members of the committee being present.

The research specialist and research interventionist and project manager will monitor AEs and severe adverse events (SAEs) as they interact with study participants. They will be documented in the study tracking database. These will be reviewed with Drs. [name] and [name] during monthly study meetings. AEs and SAEs will be reported to the KPW IRB according to the timing summarized above. AEs will be forwarded monthly and SAEs will be forwarded weekly to the DSMC.

Progress in enrollment and data collection will be reviewed on a bi-weekly basis using study status reports and status report meetings with study personnel. Any difficulties in enrollment or data collection will be discussed by the research team in order to resolve any problems and ensure complete data.

The KPWHR biostatisticians, will review all study data, including AE and CI data, once per year to determine if there are substantially more adverse events in one intervention group compared to another or if one group demonstrates a markedly superior or more negative effect on the outcome variables than the other groups. The biostatistician will provide a summary report of this review to the DSMC. If the DSMC agrees that there is a markedly superior or negative effect in one group vs. another or if there are substantially more adverse events in one group vs. another, [name] will notify the NIDA Project Officer and the KPW IRB and follow their advice about how to proceed. If the DSMC agrees that such effects are not present, no further action will be taken.

The KPW IRB will review the study protocol. The IRB will maintain ongoing oversight of the risks and benefits of the study and ensure compliance with institutional and NIH guidelines. Drs. [name] and [name] will be responsible for notifying the KPW IRB of all adverse events. The IRB will work with the Drs. [name] and [name] to ensure additional agencies (e.g., NIDA) are notified as required. Temporary or permanent suspension of an NIH funded protocol will be reported to the NIH grant program director directly responsible for the grant.

The following events will be reported to the KPW IRB within 10 business days: unanticipated medical problem, serious non-compliance, continuing non-compliance, emergency deviation from IRB approved procedures, continuation of research after IRB approval has lapsed, complaint of a subject that cannot be resolved by the study team, audit or inspection or safety-related inquiry by a federal agency, new information that indicates a new or increased risk or safety issue.

If it becomes necessary to change the proposed study protocol, amendments will be filed with the IRB at KPW seeking approval for these. These changes will be made only after receiving

approval from the IRBs. Following approval and implementation of these changes, the DSMC and NIDA program officer will be notified.

The trial may be stopped because the intervention poses unacceptable risk to participants. We will not perform interim efficacy analyses or develop related stopping rules because: 1] it is highly unlikely that the intervention will have such dramatic positive effects on both opioid dose and pain primary outcomes, 2] the comparison group receives usual care and cannot thus be harmed relative to usual care, 3] stopping early may preclude analyses of secondary outcomes and subgroup effects. The DSMC (Drs. [name], [name], and [name]) will be kept informed of AEs and SAEs encountered in the conduct of the study. They will review these yearly to determine if the intervention is posing unacceptable risks to participants. Review may occur more frequently if there are unexpectedly frequent or severe AEs. If they believe stopping the trial is appropriate, they will notify Drs. [name] and [name] and the NIDA program officer. Decisions about stopping the trial will be made in consultation with the NIDA program officer.

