### Intervention Arm

The intervention arm subjects will talk with the clinical research interventionist up to 18 times over a year on the phone. The research interventionist will:

- Train participants on methods to self-manage their pain
- Introduce and offer an optional opioid taper support
- Work with the participant's PCP to suggest medication dosage recommendations
  - Difficult cases may need to be reviewed with [name], the research physician, who may need to review pieces of the participant's medical record, specifically medication list and active diagnosis list to ensure the recommended medication dosing changes are appropriate. The research physician will not be abstracting information from the chart. [name] has Epic read only access until 12/2021, when all participants will have completed the intervention.
- Monitor, track and respond to adverse events (AE's) and Critical Incidents (CIs). CI's are a type of adverse event where a participant spontaneous reports risk behavior such as intent to harm oneself or others.

While teaching participants how to manage their pain is not part of usual care at KPWA, gradually tapering and/or discontinuing opioids are considered standard of care at KPWA and included in KPWA's "Patients on Chronic Opioid Therapy for Chronic Non-Cancer Pain Safety guidelines (September 2016). However, PCP's often do not initiate tapering due to numerous barriers such as lack of support, lack of expertise, the need to educate patients, and time constraints. As such, our trial is endorsed by the KPWA delivery system and is viewed as a mode to improve uptake of KPWA's standard of care around opioid tapering.

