After the baseline assessment and randomization, all participants will be asked to take two more surveys; 6 months after enrollment and 12 months after enrollment. The survey can be taken either in web form or on the telephone, administered by a survey research program telephone interviewer. With the 12 month phone or web survey reminder letter, all participants will receive a \$2 pre-incentive. The survey will ask questions about physical health (including any experience with pain), mental health (depression and anxiety), and medication use. All baseline, 6-month, and 12-month surveys including script are included in this packet. See Master Survey document for a list of the surveys to be administered at the three-time points.

Additionally, all subjects enrolled in the intervention who choose to taper their opioids arm will be asked to complete the two item Graded Chronic Pain Scale (GCPS) and the fourteen item Hospital Anxiety and Depression Scale (HADS) before each intervention telephone session. (See Measures for Intervention Arm only doc.). Surveys are attached in this package. The pre-visit GCPS and HADS will be completed on paper (mailed with intervention packet materials) prior to the visit and read their score to the research interventionist at the beginning of the session.

Activity	Time Commitment
----------	-----------------

Read invitation packet	5 minutes
1 st screening call	10 minutes
Read consent packet and answer any questions	10 minutes
2 nd screening call including consent and randomization	20 minutes
Baseline survey	30 minutes
Pre-visit GCPS and HADS for participants who choose to taper	5 minutes each visit 5-18
Intervention arm study visit 1-18	30-60 minutes each visit
6 month survey	20 minutes
12 month survey	20 minutes

We anticipate it will take 18 months to enroll all 250 study participants. Each participant will be followed for 12-months post randomization.

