#### Secondary data: data, sources, and date range

In addition to the primary data described above, secondary data to be collected on participants enrolled in both arms of the study are listed in the table below.

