#### Primary Data Collected on the Intervention

During each telephone session, the research interventionist will track the phone sessions into the project REDCap tracking data base hosted at KPWA. The information captured at the visits includes:

- Date of the phone visit

- Whether or not the participant attended their scheduled appointment
- Check boxes for session content that was covered during the visit
- Any critical incidents (intent to harm oneself or other)
- Any adverse events
- Detailed notes on the visit
- Amount of time spent on each visit
- HADS and GCPS score ( score read to interventionist and entered into REDCap at the beginning of each session for participants who choose to taper)

At the fourth study visit, the research interventionist will ask participants if they want to taper their opioid dosing. If the participant declines to taper, they will proceed with the rest of their pain self-management sessions and follow-up surveys. If a participant expresses interest in tapering, the interventionist will recommend medication taper suggestion to the participant's PCP using Epic Telephone Encounters. We will provide taper support at a later date if they prefer to delay the taper or resume paused tapers. Patients will be allowed to pause tapers (i.e., put the taper on hold) for any reason including the need to escalate opioid dose (e.g., surgery requiring additional pain management). Patients delaying or pausing tapers will still continue to receive the pain self-management training. Participants will be informed of the risk of stock-piling opiates during the taper process. The research interventionist may need to consult with [name], the study research physician on complicated tapering scenarios. [name] will have Epic read only access to review the medical records of any difficult tapering sessions to provide guidance to the research interventionist. The guideline for tapering was developed by [name] (UW psychiatrist and Principal Investigator), and is attached. The guidelines were reviewed by [name] (KP Medical Director, Continuum of Care), [name] (Family Medicine Physician and Medical Director, Clinical Knowledge Development and Support), [name] (Family Medicine provider, Program Chief of Family Medicine, study Co-Investigator) and [name], BCACP (Pharmacy Clinical Coordinator, Quality and Clinical Operations). This taper guideline is consistent with KPWA guidelines for COT tapering.

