### **Study Procedures –Control Arm**

#### **Sequential description**

Participants randomized to the control arm (i.e. usual care only) will not receive any intervention visits. They will only complete the three surveys described above in the “Study Procedures – Intervention Arm and Control Arm” section.

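### The yearly between-arm comparison of adverse events uses counts recorded at up to 18 intervention sessions and at no described control contact

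*Combined protocol and SAP*

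**What the plan says.** **How AEs are found.** Section 8 says that the research specialist, research interventionist and project manager "will monitor AEs and severe adverse events (SAEs) as they interact with study participants".

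**Intervention arm.** Section 4 (Intervention Arm) says: "The intervention arm subjects will talk with the clinical research interventionist up to 18 times over a year on the phone". It lists AE monitoring among the interventionist's duties. In Section 6, Primary Data Collected on the Intervention, the record kept for each session includes "Any adverse events".

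**Control arm.** Section 6, Control Arm, says of these participants: "They will only complete the three surveys described above". The entry there on monitoring or mitigating risk is N/A. The both-arm part of Section 6 does have a plan for critical incidents (intent to harm).

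**Both arms.** After baseline, "all participants will be asked to take two more surveys; 6 months after enrollment and 12 months after enrollment". These are taken on the web or with a survey-program interviewer, who is not among the AE monitors named in Section 8. Section 6 also lists "secondary data to be collected on participants enrolled in both arms of the study", including emergency and inpatient use and health plan enrolment dates from the Virtual Data Warehouse (VDW).

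**What is done with the AEs.** Section 8 has the KPWHRI biostatisticians review the data "once per year to determine if there are substantially more adverse events in one intervention group compared to another". If the Data Safety Monitoring Committee (DSMC) agrees that there is such a difference, the funder and the IRB are told. The same review looks for a markedly better or worse effect on outcomes, whereas a later paragraph of Section 8 rules out interim efficacy analyses.

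**The concern.** When events are recorded through contact, the arm with more contact records more of them. Here contact is part of the treatment, so the recorded count mixes the effect of the intervention with the effect of being asked. The comparison can suggest harm where there is none. It can also let a real excess be put down to the extra calls.

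The second risk matters because of what Section 9 expects from tapering: symptoms such as more pain, poor sleep, anxiety, sweating and nausea. Many such events come to light only when someone talks to the participant.

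**Working it through.** **1. Contacts after randomisation.** The session table in Section 6 has weeks 1 to 6 (6 sessions), weeks 8, 10, 12 and 14 (4), and weeks 18 to 46 every four weeks (8). 6 + 4 + 8 = 18, which matches Section 4. Each arm also has 2 surveys.

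| | Intervention | Control |
|---|---|---|
| Scheduled contacts with a described AE field | up to 18 | 0 |
| Surveys, AE content not stated | 2 | 2 |

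**2. If the surveys do not record AEs.** Control then has no scheduled capture and no ratio can be formed. At 4-week recall the sessions cover weeks 0 to 46, or 46 of 52 weeks, against 0.

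**3. If the surveys do record AEs.** Assume equal true risk, a constant event rate, and that an event is recorded if a contact follows within *w* weeks. Captured weeks are the part of weeks 0 to 52 lying within *w* weeks before any contact. Surveys are placed at weeks 26 and 52.

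- *w* = 4: intervention covers 0–46 and 48–52 = 50; control covers 22–26 and 48–52 = 8; 50/8 = 6.25.
- *w* = 13: 52/26 = 2.0.
- *w* = 20: 52/40 = 1.3.
- *w* = 26: 52/52 = 1.0.

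Poor attendance shrinks the ratio. If sessions stop after the ninth (week 12), *w* = 4 gives (12 + 4 + 4)/8 = 20/8 = 2.5, and *w* = 26 still gives 1.0.

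**4. A look during accrual.** The plan says: "We anticipate it will take 18 months to enroll all 250 study participants". Suppose enrolment is even over 78 weeks and the first review comes 52 weeks after the first randomisation. Follow-up among those enrolled is then uniform on 0 to 52 weeks. At *w* = 26, a control participant contributes 26 captured weeks once past week 26 and none before, so the mean is 0.5 × 26 = 13.0. With full attendance, an intervention participant is covered up to the last contact, a mean of 24.2 weeks. 24.2/13.0 = 1.9, so at this look the imbalance persists even with 26-week recall.

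**5. Precision of a VDW-based contrast.** Take 125 per arm, even enrolment over 18 months and no dropout.

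- At 12 months: 125 × (12/18) × 0.5 = 41.7 person-years per arm.
- At 24 months: 125 × [(12/18) × 1 + (6/18) × 0.75] = 114.6 person-years per arm.

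With *n* events per arm, the 95% limits multiply and divide the rate ratio by exp(1.96 × √(2/*n*)), assuming Poisson counts without overdispersion. The event rates are assumed:

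| Assumed rate per person-year | 12 months: *n*, factor | 24 months: *n*, factor |
|---|---|---|
| 0.3 | 12.5, 2.19 | 34.4, 1.60 |
| 1.0 | 41.7, 1.54 | 114.6, 1.30 |

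**The case against.** **Safety oversight does not rest on the yearly count.** AEs go to the DSMC monthly and serious ones weekly, and Section 8 allows more frequent review. The committee has a biostatistician and two pain clinicians, who can see that one arm receives calls. Over-recording in the intervention arm also errs towards caution. This stands and limits the consequence. It does not remove the problem, because the monthly and weekly reports come from the same contact-driven recording, and awareness of unequal contact gives no way to tell an artefact from a real excess.

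**The review covers all the data.** That may include VDW diagnoses and utilisation, which are collected in both arms. This stands in part: an even-handed comparison is possible, but no section makes those data the basis of the AE contrast.

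**Stronger readings that the documents do not support.**

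- A reader might infer that AEs are noted at 20 contacts in one arm and 2 in the other. No section says that the surveys record AEs. Nor does 18 against 0 prove that control captures nothing, since the instruments are not among the documents and spontaneous reports are possible.
- A reader might infer a near-certain false signal. That needs an event rate, a recall window and a significance test, none of which Section 8 gives.
- A reader might infer that a yearly VDW extract on enrolled participants is new work, because Section 5c times a VDW check at study end. That sentence concerns pregnancy codes only.
- A reader might infer that the yearly outcome check inflates the type I error. Section 8 names no test, level or boundary for it, and the template heading itself asks about benefits as well as harms. The ban on interim efficacy analyses may mean formal ones only.

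**Conclusion.** The concern holds. Followed as written, Section 8 produces a between-arm AE comparison tilted by unequal capture, with the intervention arm expected to show more recorded events at equal true risk.

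The firm figure is up to 18 described AE-recording contacts against none. The size of the distortion is not known. It is 1.0 to 6.3 over a full year, if all sessions are attended, the surveys capture AEs and recall lies between 26 and 4 weeks. Serious events are plausibly recalled longest, so the imbalance mainly concerns milder ones.

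The consequence is limited: there is no numeric trigger, escalation needs the DSMC's agreement, and the primary analysis of opioid dose and PEG is untouched. The change should be made, but the point does not threaten the trial's main result.

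The wording on superior outcomes is a minor, separate inconsistency with no demonstrated cost in type I error.

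**What to change.** **Section 8, AE comparison.** Base the between-arm safety contrast on sources collected alike in both arms: VDW emergency department visits and inpatient admissions per person-time, plus the 6- and 12-month survey measures. Outpatient visits are less suitable, because session 4 directs participants interested in tapering to book a primary care appointment. Show session-reported AEs to the DSMC as a separate intervention-arm listing that states the unequal contact, not as a between-arm count.

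**Section 8, outcome check.** Reconcile the yearly check for a superior effect with the statement that no interim efficacy analyses will be done. One clarifying sentence is enough.

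**Cost.**

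- A yearly VDW extract for enrolled participants, which the existing yearly review may already imply.
- VDW misses mild AEs; these stay in the listing.
- The first look is imprecise, with a factor of about 1.5 to 2.2 either way at the assumed rates.
- Ending person-time at withdrawal may differ slightly by arm, because the interventionist can raise matters that lead to withdrawal and control has no such contact.
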